1.2 Background and Rationale

Central adrenal insufficiency can be challenging to diagnose, as patients often present with nonspecific symptoms of weakness, malaise, and nausea. Furthermore, patients with partial adrenal insufficiency may be asymptomatic until they encounter major physiologic stress. Currently, CAI is diagnosed with basal testing and/or dynamic testing. Basal testing that reveals low morning cortisol and ACTH suggests CAI. If basal testing is equivocal, dynamic testing is typically completed with cosyntropin stimulation test. Cosyntropin stimulation testing can diagnose or rule out primary adrenal insufficiency, but can also be equivocal in CAI. The gold standard for diagnosing CAI is dynamic testing with the insulin tolerance test (ITT); metyrapone testing is also used. ITT protocol requires administration of

insulin to induce hypoglycemia, followed by serial measurements of cortisol and ACTH response. However, ITT is uncomfortable for patients and poses risks associated with hypoglycemia, such as precipitation of cardiac events or seizures. Metyrapone testing is challenging, because it requires measurement of 11-deoxycortisol, and there is often cross-reactivity between 11-deoxycortisol with cortisol in commercial immunoassays.ⁱⁱ

Secondary adrenal insufficiency is a rare diagnosis and data on mifepristone use as a diagnostic tool is unavailable in these patients. Therefore, the current study will test recruitment of this population as the primary endpoint.

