1.3 Hypothesis

With regards to the primary endpoint we propose that we can reach a target average recruitment of one patient every 6 weeks for a time study duration of 36 months.

With regards to the secondary endpoint we propose the use of mifepristone as an alternative dynamic testing reagent for CAI. Mifepristone is a glucocorticoid and progesterone receptor antagonist. In normal participants, mifepristone would be expected to cause a rise in morning cortisol. In subjects with CAI, morning cortisol will remain low. This alternative test would avoid patient discomfort associated with hypoglycemia required with insulin tolerance testing, and avoid the need to measure surrogate parameters, such as 11-deoxycortisol required with metyrapone testing.

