2 STUDY OBJECTIVES AND ENDPOINTS

2.1 Objectives

This study can be viewed as having two phases. The primary (first phase) objective of this pilot-feasibility study is to evaluate, whether recruitment of participants can be reached.

The secondary (phase II) objective is analysis of cortisol response to mifepristone in participants without history of adrenal insufficiency compared to participants with confirmed or suspected adrenal insufficiency. The cortisol response with mifepristone administration will be compared with the maximal cortisol response of the insulin tolerance test to determine whether there is any correlation between the two values.

Another objective of the study is to evaluate the effects of mifepristone on other steroid hormones and metabolites. The last objective is to determine whether there is a statistically large enough difference between the ACTH and cortisol response in healthy participants and those with adrenal insufficiency, to indicate that mifepristone could be used as an agent for diagnosis of central adrenal insufficiency.

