2.2.2 Secondary Endpoint

The secondary endpoint is the correlation between the peak cortisol measured in ITT (the gold standard) and the cortisol measured the day after mifepristone administration. We will assess whether there is a strong relationship between ITT peak cortisol and the cortisol measured after mifepristone administration. We hypothesize that the Pearson's correlation coefficient (r) for this correlation will be > 0.7 . The results of the ITT will be regarded as the gold standard in the diagnosis of secondary adrenal insufficiency. As the true cut-off for diagnosis of adrenal insufficiency using post-mifepristone cortisol is unknown we will analyze the data using ROC c-statistics for different cut-offs.

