9.2 Data Analysis

9.2.1 *Analysis Populations*

As the primary endpoint recruitment will be analyzed as a primary endpoint. The cortisol response with mifepristone administration will be compared with the maximal ITT cortisol level in all patients as a secondary endpoint. In addition, the hormone levels of participants with normal ITT will be compared to those with confirmed diagnosis of central adrenal insufficiency. Data from this study will inform planning of a larger post-pilot study.

9.2.2 *Analysis of Primary Endpoint*

The primary endpoint of this pilot feasibility study is actual study participant recruitment. Reaching the target recruitment of one participant every 6 weeks over a 36-month period (target n=26) will be regarded successful in reaching the primary endpoint. We estimate an enrollment of 90% of patients in this study. This is in accordance with our prior experience in patients with rare diseases, who are often motivated regarding study participation. We estimate a total of 85% of patients with complete data as we only anticipate minimal study drop out due to side effects of the drug or non-analyzable specimens. Study recruitment will be plotted over time and actual and target recruitment will be visually compared. We will regard a total of 22 patients as a target in meeting the primary endpoint.

9.2.3 *Analysis of Secondary Endpoints*

The secondary data point is day 2 cortisol and ACTH response to mifepristone administration. The day 2 cortisol level will be compared to the maximal ITT cortisol level to determine if and to what degree there is a correlation between the two measurements. In addition, a receiver operating characteristic (ROC) curve will be created with the day 2 cortisol level as the variable, and the ITT result as the “gold standard” test for adrenal insufficiency, to analyze the performance of cortisol as a diagnostic test. The cortisol and ACTH values in participants with normal ITT will be compared to those with confirmed diagnosis of central adrenal insufficiency, using a

t-test to determine whether there is statistically significant difference between the two populations.

9.2.4 *Analysis of Secondary Endpoints*

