The secondary end points are levels of ACTH, other (than cortisol) steroid hormones and metabolites. These hormone levels will also be analyzed with t-tests to determine whether there is a statistically significant difference between participants with normal ITT and those with confirmed diagnosis of central adrenal insufficiency.

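### Pre-dose day 1 hormones are collected, but no planned analysis specifies their use, so the secondary analyses are not set up to show the predicted cortisol rise or to separate it from a basal difference

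*Combined protocol and SAP*

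**What the plan says.** **Collection.** Sections 3 and 6.2.1 have baseline cortisol, ACTH and other steroids drawn on the morning of day 1, before the evening dose. Section 6.2.2 repeats the hormone labs on the morning of day 2. Section 6.2.1 also lets leftover ITT blood drawn before 10 AM stand in for the day 1 draw.

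**Hypothesis.** Section 1.3: "In normal participants, mifepristone would be expected to cause a rise in morning cortisol"; in CAI it is expected to stay low. Section 1.2 says of unstimulated testing: "Basal testing that reveals low morning cortisol and ACTH suggests CAI". Section 2.1 would take a large enough group difference in ACTH and cortisol response "to indicate that mifepristone could be used as an agent for diagnosis of central adrenal insufficiency".

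**Analyses.**
- Section 2.2.2 correlates the ITT peak with "the cortisol measured the day after mifepristone administration", expecting r above 0.7.
- Section 9.2.1: "The cortisol response with mifepristone administration will be compared with the maximal ITT cortisol level in all patients as a secondary endpoint".
- Section 9.2.3: "a receiver operating characteristic (ROC) curve will be created with the day 2 cortisol level as the variable", followed by a t-test: "The cortisol and ACTH values in participants with normal ITT will be compared" with those in confirmed CAI.
- Section 9.2.4, for ACTH and the other steroids: "These hormone levels will also be analyzed with t-tests".

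The word *response* appears in the synopsis and in sections 2.1, 9.2.1 and 9.2.3 without a definition.

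**The concern.** The predicted rise is a within-person quantity. A comparison of levels between groups on one day does not show it. If people with CAI already have lower morning cortisol before the drug, a day 2 ROC curve or t-test can look favourable partly or wholly for that reason. Everyone is treated (section 5.1), so the day 1 value is the only reference inside the study.

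At stake is what the pilot hands to the post-pilot study: whether cortisol rises, by how much in each group, and whether the day 2 value carries more than an ordinary morning cortisol does.

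**Working it through.** **1. The plan's own figures.** 36 months is about 156.5 weeks; 156.5 / 6 = 26.1, which gives the target of 26. 26 × 0.85 = 22.1, which gives 22 with complete data. Both reproduce. The plan gives no SD, effect size or power for the cortisol analyses, so nothing further can be reproduced.

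**2. Which day each analysis uses.**

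| Analysis | Section | Variable stated |
|---|---|---|
| Correlation with ITT peak | 2.2.2, 7.2, 9.2.3 | post-dose (day 2) cortisol |
| ROC curve | 9.2.3, synopsis | day 2 cortisol level |
| t-tests, cortisol and ACTH | 9.2.3 | values, no day |
| t-tests, ACTH and other steroids | 9.2.4 | levels, no day |
| c-statistics, exploratory | 2.2.3, 7.3 | no day |

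None names a day 1 value, a change, a paired analysis or a day 1 ROC curve.

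**3. What a basal difference alone can produce.** All inputs here are assumed: a basal group difference of d SD, no added separation by the drug, and every completer having an ITT peak. The split is 11 v 11 (half of 22), or 8 v 8 if only 16 of 22 have an ITT. With equal-variance normal values (on the log scale if cortisol is log-normal), AUC = Φ(d/√2). The day 2 t-test has noncentrality d√(n₁n₂/(n₁+n₂)), which is 2.345d at 11 v 11 and 2d at 8 v 8 (two-sided 5%).

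| d | Day 2 AUC | Significant, 11 v 11 | Significant, 8 v 8 |
|---|---|---|---|
| 0.3 | 0.58 | 10% | 9% |
| 1.0 | 0.76 | 61% | 46% |
| 2.0 | 0.92 | 99% | 96% |

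**4. What using day 1 would add.** I simulated 20,000 trials per cell with log-normal cortisol, normal-group geometric mean 14, log SD 0.3 or 0.5, and day-to-day correlation 0.5 to 0.9 (all assumed). Rejection rates are for 11 v 11.

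- *Change scores.* At d = 1, an equal 1.5-fold rise in both groups makes a t-test on the absolute change reject in about 11% to 30% of trials, and on the log change in 5%. An equal rise of 5 units reverses this: the log change rejects in about 12% to 30% and the absolute change in 5%. Neither scale alone is free of the basal difference.
- *Paired AUC difference, day 2 minus day 1.* It averages 0.00 when the drug adds no separation. If only normals rise 1.5-fold, it averages 0.19 or 0.14 (log SD 0.3 or 0.5) at d = 1, but only 0.06 to 0.07 at d = 2, because the AUC is near its ceiling. In that scenario at 11 v 11 the day 2 AUC equals exactly 1 in 4% to 16% of trials at d = 1, and in about a third to three fifths at d = 2. DeLong's variance for that AUC is then zero.
- *Precision at d = 1, no drug effect.* The SD of the paired difference at correlation 0.9 and 0.5 is 0.055 and 0.110 (11 v 11), or 0.067 and 0.130 (8 v 8). Multiplying by 1.96 gives half-widths of 0.11 to 0.22 and 0.13 to 0.25.

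**The case against.** **The wording may already imply change.** Sections 2.1 and 9.2.3 speak of response, the exploratory endpoints concern the drug's impact, the labs are called baseline and repeat, and section 6.2.3 holds the morning glucocorticoid until after both draws. That fits an intended paired use. It stands to this extent: the team may mean to use day 1, and the undated t-tests do not exclude it. But no sentence says so, and wherever the correlation or ROC variable is spelled out it is the post-dose level.

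**The rise is already known.** Section 1.4 reports a dose-dependent rise in morning ACTH and cortisol in earlier studies, so a wholly inert drug is not what the documents suggest. That stands. Section 1.2, however, says data on diagnostic use in these patients are unavailable, so the rise in CAI is not known, and an equal rise in both groups gives the same AUCs as an inert drug.

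**A diagnostic test may use a post-drug level.** True. The stated comparator is ITT, and no endpoint asks for gain over basal cortisol. Section 1.2 places dynamic testing after equivocal basal testing. This is why the within-person change, which is the protocol's own hypothesis, should lead, with the AUC comparison as support.

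**It is a small pilot and the samples will exist anyway.** Also true, and it limits the weight of the point. Adding the analysis later would mean choosing the scale and the handling of odd baselines after seeing the data.

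**Conclusion.** The point holds in a limited form. Day 1 hormones are collected, no analysis specifies their use, and the secondary analyses as specified are not set up to show the predicted rise or to separate day 2 discrimination from a basal difference. The impact is minor to moderate: it touches secondary and exploratory aims and planning data, and leaves the recruitment endpoint alone. The illustration rests wholly on assumed inputs. Its range, from 10% to 99% significant at 11 v 11, shows what is possible, not how large the effect is here.

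A reader might infer more, and the documents do not support it:
- *That the results will show neither a rise nor any gain.* The undefined *response* and the undated t-tests leave room for day 1 to be used.
- *That the day 2 level is the wrong variable.* It is a legitimate one and matches the stated endpoint.
- *That a day 1 comparison would prove a drug effect.* With no untreated arm it would support attribution, not prove it.

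**What to change.** In sections 9.2.3 and 9.2.4:

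1. Keep the day 2 correlation and ROC curve as the secondary analyses. State that *response* there means the day 2 level, and give the day for every t-test.
2. As the main addition, report the within-person day 1 to day 2 change in cortisol and ACTH by ITT group, and the between-group difference in change, with 95% CIs. Give it both as a difference and as a ratio.
3. Beside the day 2 results, show descriptively the day 1 AUC, the correlation of day 1 cortisol with ITT peak, and the paired AUC difference. Use an interval that stays valid when an AUC is at or near 1, not DeLong alone. Note that this difference is insensitive when basal discrimination is already high.
4. Report how many participants have both an ITT peak and a day 1 value, since the third inclusion criterion admits people without an ITT. Flag baselines from leftover ITT serum (at least a week before mifepristone testing, drawn up to 10 AM) and any overnight use of the rescue dexamethasone in section 6.2.3, and repeat without them.

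**Cost.** Some extra analysis text and no new samples. The estimates will be imprecise, as the half-widths above show, so they inform planning of the post-pilot study and do not settle the question.

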10 MONITORING

To assure adequate protection of the rights of human subjects, per 21 CFR §312.50, 312.53, this study will be monitored by the University of Michigan Institute for Clinical and Health Research (MICHR). Routine monitoring will be scheduled at appropriate intervals, with more frequent visits occurring at the beginning of the study. An initiation visit will take place, followed by routine monitoring visits. Additional visits can be scheduled at the request of the Project Manager.

The established monitoring plan will ensure the quality and integrity of the data through pre- investigation visits and periodic site visits to verify adherence to the protocol, completeness and accuracy of study data and samples collected, proper storage, dispensing and inventory of study medication, and compliance with regulations.

11 DATA HANDLING AND RECORD KEEPING

11.1 CRFs / Electronic Data Record

Data will be protected by several different measures throughout the life of the study. Paper documents and records will be stored in a secured location with restricted access to authorized personnel only. Electronic study documents and data will be kept in a password protected environment, whereby access rights will be terminated at the request of the PI when study members leave the project.

11.2 Record Retention

Per 21 CRF §312.62, study records will be retained for 2 years after the investigation is discontinued.

12 ETHICS

12.1 IRB/FDA

Prior to study commencement, an Investigator Initiated Investigational New Drug (IND) will be submitted to the Food and Drug Administration (FDA), for review and approval. Prior to study commencement, an Investigator Initiated Investigational New Drug (IND) will be submitted to the Food and Drug Administration (FDA), for review and approval. The study will also be reviewed and approved by the Institutional Review Board (IRBMED, University of Michigan, Ann Arbor, MI).

12.2 Institutional Review Board (IRB)

Before implementing this study, the protocol, the proposed informed consent form and other information to be provided to subjects, must be reviewed by a properly constituted Institutional Review Board (IRB). Any amendments to the protocol must be reviewed and approved by IRBMED.

12.3 Subject Information and Consent

The study team member will explain to each subject (or legally authorized representative) the nature of the study, its purpose, the procedures involved, the expected duration, the potential risks and benefits involved and any discomfort it may entail. Each subject will be informed that participation in the study is voluntary and that he/she may withdraw from the study at any time and that withdrawal of consent will not affect his/her subsequent medical treatment or relationship with the treating physician.

This informed consent will be given by means of a standard written statement, written in non-technical language. The subject should read and consider the statement before signing and dating it, and should be given a copy of the signed document. If the subject cannot read or sign the documents, oral presentation may be made or signature given by the subject's legally appointed representative, if witnessed by a person not involved in the study, mentioning that the patient could not read or sign the documents. No patient can enter the study before his/her informed consent has been obtained.

The informed consent form is considered to be part of the protocol, and will be submitted for IRB approval.

12.4 STUDY DISCONTINUATION CRITERIA

12.4.1 *Stopping Rules for Safety reasons*

There will be no Data Safety Monitoring Board as this is a single site study.

However, we will continuously review SAE. If a study related SAE occurs in 3 of 6 patients or in >50% of patients at any time, the study will be terminated.

12.4.2 *Rules for Discontinuation of a Subject*

In the event a patient drops out of the study or is discontinued due to protocol violations, all attempts will be made to exit the patient in accordance with the protocol requirements.

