12.4 STUDY DISCONTINUATION CRITERIA34
12.4.1 STOPPING RULES FOR SAFETY REASONS34
12.4.2 RULES FOR DISCONTINUATION OF A SUBJECT34
13 REFERENCES35

List of Tables

Table 1. Schedule of Activities.....22

PROTOCOL SYNOPSIS

Financial Sponsor: Corcept Therapeutics, Inc.
Name of Finished Product: Mifepristone (Korlym)
Study Title: Mifepristone Dynamic Testing for Diagnosis for Central Adrenal Insufficiency
Study Phase: Phase II
Primary Objective: Phase I of the study is to determine whether recruitment at our institution is sufficient for a study for mifepristone use as a diagnostic tool to diagnose central adrenal insufficiency and to generate data to inform a post-pilot study. Phase II of the study involves taking those recruited and having them complete the study to generate the data.
Study Design: Single-center pilot feasibility study of mifepristone to evaluate the recruitment of participants with the diagnosis of confirmed or suspected secondary adrenal insufficiency. Cortisol (secondary endpoint), ACTH and other steroid responses (exploratory endpoints) to mifepristone in participants with normal insulin tolerance testing (ITT) and participants with confirmed or suspected adrenal insufficiency will be analyzed. The study will test primarily for feasibility of recruitment (phase 1) and provide preliminary data for planning a post-pilot study (phase 2).
Study Population: Subjects with normal ITT and subjects with confirmed or suspected diagnosis of central adrenal insufficiency.
1. Criteria for Inclusion and Exclusion: Please see section 4.
Test Product; Dose; and Mode of Administration: Single dose of mifepristone 600mg, administered orally
Reference or Placebo Therapy; Dose; and Mode of Administration: None
Duration of Treatment: One day
Variables: Cortisol, ACTH

Statistical Methods:

- For the primary endpoint of recruitment actual recruitment will be compared to target recruitment (1 patient per 6 weeks). Actual and target recruitment per month will be plotted and visually compared. Recruitment of ≥ 26 participants and study completion and complete data on ≥ 22 patients will be a success regarding the primary endpoint.
- For the secondary endpoint the day 2 cortisol level will be compared to the maximal ITT cortisol level to determine if and to what degree there is a correlation between the two measurements.

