4.1.1 Inclusion Criteria

Adult (ages ≥ 18 years of age) male and female subjects who:

1. Completed ITT at University of Michigan from 2012 to present.
OR
2. Are scheduled to complete ITT.
OR
3. Are clinically suspected to have adrenal insufficiency but have not undergone ITT.

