5 STUDY TREATMENTS

5.1 Allocation to Treatment

All subjects will be in the treatment group.

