5.3 Drug Supplies-Mifepristone

- Other names for the drug: KORLYM®, C1073, RU486
- Description: 300 mg tablets are light yellow to yellow, oval-shaped, film-coated tablets debossed with “Corcept” on one side and “300” on the other. Each bottle contains 28 tablets.
- Mode of action: Mifepristone is a selective antagonist of the progesterone receptor at low doses and blocks the glucocorticoid receptor (GR-II) at higher doses. Mifepristone has high affinity for the GR-II receptor but little affinity for the GR-I (MR, mineralocorticoid) receptor.

- Pharmacokinetics:

Absorption

Following oral administration of mifepristone to healthy volunteers, time to peak plasma concentrations of mifepristone occurred between 1 and 2 hours following single dose, and between 1 and 4 hours following multiple doses of 600 mg. The mean plasma concentrations of the three active metabolites of mifepristone peak between 2 and 8 hours after multiple doses of 600 mg/day, and the combined concentrations of the metabolites exceed that of the parent mifepristone. Exposure to mifepristone is substantially less than dose proportional. Time to steady state is within 2 weeks, and the mean (SD) half-life of the parent mifepristone was 85 (61) hours following multiple doses of 600 mg/day of mifepristone. Studies evaluating the effects of food on the pharmacokinetics of mifepristone demonstrate a significant increase in plasma levels of mifepristone when dosed with food.

Distribution

Mifepristone is highly bound to alpha-1-acid glycoprotein (AAG) and approaches saturation at doses of 100 mg (2.5 µM) or more. Mifepristone and its metabolites also bind to albumin and are distributed to other tissues, including the central nervous system (CNS).

Metabolism

Cytochrome P450 3A4 (CYP3A4) has been shown to be involved in mifepristone metabolism in human liver microsomes. Two of the known active metabolites are the product of demethylation (one monodemethylated and one di-demethylated), while a third active metabolite results from hydroxylation (monohydroxylated).

Elimination and Excretion

Excretion is primarily (approximately 90%) via the fecal route. Excretion in the urine accounts for less than 10%.

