6.2.3 Subjects with history of adrenal insufficiency

Subjects with confirmed history of adrenal insufficiency (AI) on glucocorticoid replacement at baseline will be instructed on the following protocol for glucocorticoid dosing during testing. All components of the study protocol are otherwise the same as above.

- Day 0: Take the morning dose of glucocorticoid and hold the afternoon dose.
 - Day 1: Hold the morning dose until labs are drawn, then take the morning dose.
Hold the afternoon dose.
 - Day 2: Hold the morning dose until labs are drawn, then take the morning dose and resume baseline dosing schedule.
-
- Withholding afternoon doses of glucocorticoids for testing is routinely done in clinical practice and considered safe. Participants with diagnosed AI will be provided with a prescription for 4 mg of dexamethasone. Participants will be

provided with two 24-hour phone numbers to call if/when they experience any side effects. . Participants will be instructed to take 4mg of dexamethasone in case they experience significant signs of acute adrenal insufficiency [increasing nausea, lethargy, diarrhea, fever]. Participants are encouraged to contact one of the 24-hour phone numbers prior to taking the dexamethasone and are advised to call the number after taking the dexamethasone. As participants are scheduled for a blood draw the next morning they will be clinically assessed for adrenal insufficiency in case overnight concerns occur and further management will depend on this clinical evaluation. On day 2, participants with adrenal insufficiency will resume their usual dose of hydrocortisone replacement therapy and occurrence of adrenal insufficiency will become less likely. However, participants will remain advised to keep the dexamethasone emergency dosing and to contact the study team in case of any symptoms and signs of adrenal insufficiency

Table 1. Schedule of Activities

Protocol Activity	Screening Phone Call	Screening / Day 1^a	Day 2	Day 7 (+/- 3 days) Phone Call	Day 30 Phone Call (+/- 3 days)
Visit # / Phone call	1	1	2	3	4
Informed Consent		X			
Medical History	X	X			
Vitals Signs^b		X	X		
Serum Chemistry^c		X	X		
Complete Blood Count		X	X		
Pregnancy Test^d	X	X			
Hormone Labs^e		X	X		
Treatment with study agent (10 pm)		X			
Adverse Event Assessment		X	X	X	X

- a. There will be at least a one-week interval between ITT and mifepristone testing.

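### Section 12.4.1 counts related SAEs over everyone dosed, so harm confined to diagnosed adrenal insufficiency can be diluted; one added sentence is a cheap, low-severity improvement

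*Combined protocol and SAP*

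**What the plan says.** Section 12.4.1 has no Data Safety Monitoring Board and relies on continuous review of SAEs. Its numerical rule is that, if a study-related SAE occurs "in 3 of 6 patients or in >50% of patients at any time, the study will be terminated". No subgroup is named, and the rule does not say whether the six are the first six, six in a row, or any six.

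The denominator is mixed by design. Section 5.1 states "All subjects will be in the treatment group", and the synopsis describes the population as "Subjects with normal ITT and subjects with confirmed or suspected diagnosis of central adrenal insufficiency". Section 4.1.1 also admits people who "Are clinically suspected to have adrenal insufficiency but have not undergone ITT".

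Section 6.2.3 sets one group apart. "Subjects with confirmed history of adrenal insufficiency (AI) on glucocorticoid replacement at baseline" follow a schedule of held doses, and "Participants with diagnosed AI will be provided with a prescription for 4 mg of dexamethasone". They also receive two 24-hour phone numbers. Section 5.3 notes that the drug "blocks the glucocorticoid receptor (GR-II) at higher doses".

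**The concern.** The plan recognises a specific hazard in participants with diagnosed AI: replacement doses are held around a dose of a glucocorticoid-receptor blocker, with rescue medication supplied. Harm is nevertheless counted over all participants, including those with a normal ITT who do not share that hazard. If related SAEs cluster in the AI group, participants without them enlarge the denominator. Whether the study stops then depends partly on the mix of participants and the order of entry, as well as on the risk in the exposed group. This is the only numerical study-level stop in the documents, and no independent board stands behind it.

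**Working it through.** **Inputs from the documents.** The plan states no operating characteristics for the rule, so only the sample size can be reproduced. Section 9.2.2 counts recruitment "over a 36-month period (target n=26) will be regarded successful". One participant per 6 weeks over 36 months is 156/6 = 26, and 26 × 0.85 = 22.1 matches the target of 22 complete. Section 4.1 gives n = 20; the pattern is the same at that size.

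**Assumptions, not in the documents.** N = 26; random entry order; diagnosed-AI share *s* of 25, 30, 40 or 50%; related SAE risk *q* in AI participants and none in others; the percentage limb applied literally from participant 1.

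**Step 1: dilution in the three-of-six limb.** In the pooled count, the chance that a given participant has an SAE is r = s × q. With s = 0.40 and q = 0.50, r = 0.20, and P(X ≥ 3 | 6, 0.20) = 0.099. For six AI participants alone, P(X ≥ 3 | 6, 0.50) = 1 − (1 + 6 + 15)/64 = 0.656.

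**Step 2: the percentage limb.** The expected pooled rate is s × q. If fewer than half of those treated have AI, the final pooled rate cannot exceed 50% even if every AI participant has an SAE: 7 of 26 is 27%. The limb can still fire early by order of entry, since one SAE in participant 1 is 1/1. At r = 0.20, both limbs together stop 26.5% of trials, of which 20 points come from participant 1 alone.

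**Step 3: both limbs, SAEs in half of AI participants (q = 0.50).** The pooled rule is computed exactly by recursion over 26 ordered participants. Cells with the AI-only sentence are simulated (200,000 trials each).

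| Probability of stopping, % | s = 25% | 30% | 40% | 50% |
|---|---|---|---|---|
| r = s × q | 0.125 | 0.15 | 0.20 | 0.25 |
| Pooled, first six | 14.9 | 18.5 | 26.5 | 35.5 |
| Pooled, any six consecutive | 31.5 | 42.1 | 62.5 | 78.8 |
| Pooled, any three once six are treated | 67 | 78 | 92 | 98 |
| AI-only count alone | 56 | 63 | 69 | 72 |
| First six plus AI-only sentence | 59 | 66 | 72 | 76 |
| Any six consecutive plus AI-only sentence | 60 | 68 | 78 | 86 |

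Under first six, the pooled rule trails the AI-only count at every share shown. Under six consecutive, the gap is clear at 25–30%, small at 40%, and reversed at 50%. Under any three, the pooled rule is the more sensitive throughout and the AI-only sentence is redundant.

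**Step 4: other SAE rates.** If every AI participant has an SAE, first six stops 36/45/67/86% across the four shares, six consecutive 79/90/98/99.9%, and the AI-only count 97/99/100/100%. At q = 0.20, first six stops about 5–11%, rising to 12–18% with the sentence.

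**Step 5: sensitivity.** With a 2% SAE rate in other participants and q = 0.50, first six with the literal percentage limb stops 15/24/27% at shares of about 25/33/40%. Counting the percentage limb only from the sixth participant, it stops 3/8/10%. If 30% have diagnosed AI and a further 20% are suspected cases with the same risk, r = 0.50 × 0.50 = 0.25, and the pooled rule stops 36% (first six) or 79% (six consecutive).

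**Step 6: unnecessary stops added by the sentence (shares 30–50%).** At a 5% AI risk it adds 0.13–0.17 points to first six and 0.08–0.13 to six consecutive. At 10% it adds 1.0–1.2 and 0.6–0.9. For reference, P(X ≥ 3 | 6, 0.05) = 0.002 and P(X ≥ 3 | 6, 0.10) = 0.016.

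**The case against.** The strongest reply is that the size rests on what the plan leaves open. No AI share is stated, and because one search route in section 4.1 is a listed diagnosis of AI, a share above 25–40% is plausible. Suspected cases take the same receptor blocker and may share the risk, which narrows the gap. One reading of the six gives no dilution. The large gains need SAE rates of 50% or more after a single dose with rescue dexamethasone available; at 20% the rule mostly stays silent even with the extra sentence. All of this stands and sets the severity at low.

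A reader might infer that the AI group has no effective protection. The documents do not support that. Section 6.2.3 gives rescue medication, 24-hour numbers and next-morning assessment; section 8.2.1 requires notification of SAEs to the principal investigator within one business day and covers IRB and FDA reporting; section 12.4.1 adds continuous review. These safeguards reduce the practical risk, but none gives the exposed group a stopping threshold.

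A reader might also infer that the six should simply be defined as any six consecutive patients. That is a trade-off. If the sponsor meant any three once six are treated, the definition weakens the rule: even with the AI-only sentence, 60/68/78/86% against 67/78/92/98%. If the first six was meant, it raises stops from 11% to 22% when all participants carry a 10% risk.

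**Conclusion.** The point holds as a cheap, low-severity improvement. Pooling and the undefined six are both in the text. Material dilution depends on the reading: first six with an AI share up to about 50%, or six consecutive with a share of about 25–33%. The share, the SAE rates and the absence of SAEs in other participants are assumptions. The documents do not show that the existing rule would fail in this trial. The additive sentence is worth having because it can never reduce protection, whichever reading was intended.

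**What to change.** Leave the pooled rule as it is and add to section 12.4.1:

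> *In addition, counting only participants with diagnosed AI (those given the 6.2.3 dexamethasone prescription), the study will be terminated if a study-related SAE occurs in 3 of the first 6 such participants, or in >50% of them once at least 6 have been treated.*

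Separately, ask the sponsor to state which six it intended, without imposing a definition.

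The sentence needs one extra running count on data already collected, with no new patients, visits or tests. Membership is known before dosing. At one participant per 6 weeks (42 days) with the last call at Day 30 ± 3, the count can usually be updated before the next dose. The price in unnecessary stops is that of step 6. The start at the sixth AI participant must stay in the wording: without it, one SAE in the first AI participant ends the study, and the AI-only count would fire in about 5% of trials at a 5% AI risk and 11% at 10%. Suspected cases without the prescription remain covered by the pooled rule only.
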